### **6.2 Exclusion Criteria**

Subjects meeting any of the following criteria will be excluded from this study;

- 1) Those with serious cardiac, pulmonary, hepatic, and renal dysfunctions, unable to tolerate the surgery;
- 2) Those with uncontrollable neurological or psychiatric diseases or mental disorders, poor compliance, and being unable to cooperate and describe the treatment response.
- 3) Those who are going to undergo emergency surgery or palliative surgery due to lung

abscess or hemoptysis.

- 4) Those who have been treated, or are undergoing neoadjuvant or induction radiotherapy or targeted therapy.
- 5) Those who have a combined history of other malignant tumors
- 6) Those who have a history of thoracic surgery
- 7) Those who are pregnant or breastfeeding women
- 8) Patients of childbearing age who refuse to use contraception.

### **6.3 Recruitment**

Source of study subjects: outpatients

Recruitment location: Thoracic Surgery and Respiratory Medicine Clinic of participant centers.

Recruitment method: Through WeChat public number, departmental website and other online channels to publish recruitment information.

The researchers conducted a study on the lungs of patients attending outpatient clinics. After preliminary evaluation of lung cancer patients in the outpatient clinic of Ruijin Hospital and identification of those who are potentially eligible for enrollment, as well as improvement of chest CT, PET-CT (optional), cardiac ultrasound, lung function and other auxiliary examinations, and after it is clear that they are eligible for enrollment, subjects will be informed of the study and will sign an informed consent form.

Measures to strengthen the compliance of the study subjects: The researchers contacted the study subjects or their families through the Internet or telephone, informing them of the schedule of the treatment program and reminding them of the follow-up visits.

### **6.4 Methods of Study Subject Allocation**

This study is a single-arm clinical trial and does not involve the allocation of study subjects to the enrollment group.

## **7. Research interventions**

### **7.1 Giving the research intervention**

#### **7.1.1 Description of the research intervention**

After the patients were enrolled in the group, further relevant examinations (bronchoscopy, chest enhanced CT, PET-CT (optional), cranial MR, cardiac ultrasound, pulmonary function, electrocardiogram, and blood test) were completed, contraindications to surgery were ruled out, and they were evaluated to receive neoadjuvant/induced chemo-immunotherapy after multidisciplinary discussion (thoracic surgery, respiratory medicine, pathology). After completion of treatment, the patient is reassessed and discussed multidisciplinary for surgical feasibility. Open or minimally invasive (thoracoscopic-assisted, robotic-assisted) radical lung cancer surgery with systemic lymph node dissection is performed, including

pneumonectomy, lobectomy, combined lobectomy, and sleeve lobectomy (with or without pulmonary angioplasty/sleeve). Based on the surgical pathology and guidelines, the postoperative adjuvant treatment and follow-up plan was individualized after multidisciplinary discussion.

### **7.1.2 Dosage and method of administration**

No drug trials were involved in this study.

### **7.1.3 Methods of establishing, preserving, and unblinding test drug codes and breaking the blind in emergency situations**

This study does not involve blinding.

### **7.1.4 Items and number of clinical and laboratory examinations to be conducted**

Postoperative follow-up in January, follow-up in March, follow-up every three months thereafter, and follow-up every six months after one year postoperatively, with blood routine, biochemistry, tumor indexes, and chest CT examination at each follow-up. In the first year after surgery, head MR was performed every half a year and PET-CT (optional) was repeated every year; after one year after surgery, head MR was performed every half a year and PET-CT (optional) was performed every year.

## **7.2 Preparation/handling/storage/responsibility**

### **7.2.1 Responsibility**

No drug trials were involved in this study.

### **7.2.2 Composition, appearance, packaging and labeling**

This study did not involve drug testing.

### **7.2.3 Product storage and stability**

This study does not involve drug testing.

### **7.2.4 Preparation**

This study does not involve drug trials.

## **7.3 Measures to reduce bias: randomization and blinding**

This study was a single-arm study and did not involve randomization grouping and blinding.

## **7.4 Follow-up and compliance**

The patients will be followed up in one and three months after surgery. Then every three months in first year, every six months after one year of operation, with blood routine, biochemistry, tumor indexes, and chest CT examination at each visit. Within one year after surgery, head MR was performed every six months and PET-CT was performed at one year, and after one year after surgery, head MR was performed every six months and PET-CT was performed every year.

The researchers will contact the study participants or their families via the Internet or telephone to inform them of the treatment schedule and remind them of follow-up visits.

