**Study interventions :**

[figure not shown]
Patients enrolled will further undergo relevant examinations (including chest enhancement CT, PET-CT (optional), cranial MR, bronchoscopy, cardiac ultrasound, pulmonary function, electrocardiogram, and blood tests) and be checked for contraindications to surgery, then be evaluated whether be

amenable to surgical treatment after multidisciplinary discussion (Department of thoracic surgery, department of respiratory medicine, department of radiology). Open or minimally invasive radical lung cancer surgery and systematic lymph node dissection will be performed on eligible patients. The perioperative complications, lymph node dissection, R0 clearance rate, 3-year event-free survival rate, overall and disease-free survival time, quality of life, and pulmonary function will be recorded and analyzed.

**Study duration :** 5 years

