**Duration of subject participation : 3 years**

### 1.2 Technology roadmap

## 2. Background of the Study

### 2.1 Significance of the study

Lung cancer is one of the most common malignant tumors worldwide, and the number of new lung cancer cases is expected to be as high as 1.8 million worldwide in 2019 [1]. The mortality rate of lung cancer is the highest among malignant tumors, and one-fifth of all malignant tumor deaths worldwide are due to lung cancer [1].

In recent years, lobectomy is no longer the only option for some early-stage lung cancer patients. Sub-lobe resection can achieve better protection of lung function with the same prognosis. Meanwhile, with the gradual development of targeted therapy, immunotherapy and other treatment modalities, more patients benefit from preoperative tumor downstaging. However, pneumonectomy is still preferred as the first choice for operable patients with tumors invading the main pulmonary artery and main bronchus, even achieving tumor downstaging after neoadjuvant therapy. Pneumonectomy is often associated with higher rates of perioperative complications and mortality than lobectomy, and a higher proportion of patients undergoing total pneumonectomy are lost to postoperative adjuvant therapy, which may have an impact on long-term survival. There is currently no evidence to support the decision to convert to lobectomy in this population.

We propose to conduct a single-arm prospective clinical study to investigate the feasibility, safety, perioperative and long-term outcomes of surgery (converting to lobectomy of pneumonectomy) in patients with locally progressive operable non-small cell lung cancer after neoadjuvant therapy.

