## 5. Research design

### 5.1 Overall design

In this single-arm, open-label, multicenter, prospective clinical trial, 50 cases of operable non-small-cell lung cancer requiring pneumonectomy were proposed to be enrolled. Patients will be treated with neoadjuvant or inductive combination therapy of immuno- and chemo- by evaluation from multidisciplinary discussion (Department of Thoracic Surgery, department of Respiratory Medicine, department of Radiology), than undergo open or minimally invasive radical surgery for lung cancer and systematic lymph node dissection. Peri-operative complications, lymph node dissection, R0 resection rate, and postoperative short-term and long-term efficacy outcomes will be recorded and evaluated.

Participating centers:

- 1 Ruijin Hospital, Shanghai Jiao Tong University School of Medicine, Shanghai, China
- 2 Shanghai General Hospital of Shanghai Jiao Tong University School of Medicine
- 3 The Ninth People's Hospital of Shanghai Jiao Tong University School of Medicine
- 4 Huadong Hospital, Fudan University Medical College, Shanghai, China

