### **5.3 Determination of sample size**

This study is a prospective observational clinical study, and the purpose of the study is to evaluate the feasibility and long-term outcome of pneumonectomy to lobectomy after neoadjuvant or induction chemoimmunotherapy for locally progressive non-small cell lung cancer. Due to the lack of previous reference data, the sample size was not calculated based on hypothesis testing, and 50 patients were enrolled.

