## 8. Discontinuation of the research intervention and discontinuation/withdrawal of research subjects

### 8.1 Discontinuation of the research intervention

The investigator should consider discontinuing the study intervention if the subject develops.

1) patients with serious unintended adverse reactions or complications that do not improve significantly after symptomatic treatment and cannot be continued. patients who are unable to continue the study intervention.

2) Patients who are unable to tolerate the study intervention for non-treatment related reasons.

3) Laboratory test values that, in the judgment of the investigator, are clinically significant. After discontinuation of the study intervention, patients may continue to complete other parts of the treatment regimen, including chemotherapy, radiotherapy, targeted therapy, immunotherapy, etc., and will be treated in accordance with the study protocol. therapy, targeted therapy, immunotherapy, etc., and will be scheduled for examination and follow-up according to the study protocol.

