#### Secondary study endpoints

- 1) Lymph node dissection: Record the total number of lymph node dissection, the number of stations of lymph node dissection, and the number of lymph node dissection at each station during the operation, and evaluate them according to the pathologic results.
- 2) Perioperative indicators: Record the duration of surgery, intraoperative bleeding, the incidence of intraoperative accidents, evaluated by surgical records and perioperative clinical manifestations, laboratory tests, physical examination;
- 3) Postoperative short-term efficacy indicators: record the length of postoperative hospitalization (days), survival within 30 days after surgery, and evaluate through postoperative follow-up;
- 4) Perioperative complication rate: Evaluated by clinical manifestations, laboratory tests, and physical examination.
- 5) 3-year disease-free survival rate: defined as the proportion of patients without tumor recurrence or metastasis 3 years after surgery, evaluated by postoperative follow-up.
- 6) 3-year overall survival rate: defined as the proportion of patients who are still alive 3 years after surgery, and evaluated by postoperative follow-up.

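### Visits and both defined 3-year survival rates start at surgery although enrolment precedes chemoimmunotherapy, so enrolled patients never operated on have no time zero, and the abstract's event-free survival is left undefined

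*Protocol*

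**What the plan says.** **Order of events.** Section 5.1 proposes to enrol 50 patients and continues: "Patients will be treated with neoadjuvant or inductive combination therapy of immuno- and chemo- by evaluation from multidisciplinary discussion"; surgery comes after that. Section 7.1.1 has the same order. After enrolment and work-up, "they were evaluated to receive neoadjuvant/induced chemo-immunotherapy after multidisciplinary discussion", and once treatment is complete a second multidisciplinary discussion decides whether surgery is feasible.

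**Visits.** Section 7.4 opens: "The patients will be followed up in one and three months after surgery". Its later visits, and those of 7.1.4, are also counted from the operation. The table in 7.5 passes from screening to the peri-operative period, with no column for the chemoimmunotherapy phase.

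**Survival endpoints.** Section 9.1 gives 3-year OS as "defined as the proportion of patients who are still alive 3 years after surgery" and dates 3-year DFS from surgery as well. Section 5.2 lists OS and DFS in months without a time origin, and 10.2 adds none.

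**Event-free survival.** The abstract (1.1, study interventions) promises a "3-year event-free survival rate". The term does not recur in 5.2, 9.1 or 10.2.

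**Patients who stop early.** Section 8.1 says that after discontinuation patients "will be scheduled for examination and follow-up according to the study protocol". Section 8.2 has the reason for withdrawal, which may be progression, entered on the case report form. Section 8.3 provides 3 years of telephone and outpatient follow-up.

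**Participation.** The abstract states "Duration of subject participation : 3 years", with no starting point.

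**The concern.** A strategy that starts with systemic treatment and aims at a smaller resection can fail before the operation, through progression, death or a patient who stays or becomes inoperable. The reassessment in 7.1.1 exists because this can happen. If the survival clock starts only at surgery, these failures are not counted against the strategy. The 3-year OS then describes patients who got through the pre-operative phase, while a reader may take it as the outlook for a patient entering the study.

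The event-free survival in the abstract is the kind of measure that would show such failures, yet it has no definition, time origin or analysis. Status before surgery that is not collected prospectively may be hard to recover later.

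**Working it through.** **No figure to reproduce.** The protocol says that "the sample size was not calculated based on hypothesis testing, and 50 patients were enrolled". It states neither the share expected to miss surgery nor an expected survival rate. The check is therefore a comparison of sections, followed by an illustration on stated assumptions.

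**Step 1: follow one patient through the text.** Take a patient enrolled under 5.1 who receives chemoimmunotherapy and is then found not to be operable.

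- Visits in 7.1.4, 7.4 and 7.5: all follow-up is counted from the operation, so no visit date can be set.
- 3-year OS and DFS in 9.1: counted from the operation, so the patient has no time zero and cannot enter either rate.
- OS and DFS in months (5.2, 10.2): no origin stated, so inclusion is undetermined.
- Follow-up promised in 8.1: it refers to the protocol's schedule, which leads back to the operation.
- Follow-up in 8.3: contact is promised, but the date from which it is counted is not given.
- Event-free survival: named in the abstract, defined nowhere.
- Replacement in 8.2: subjects who did not receive the study intervention are replaced. If that term means surgery, this patient is replaced as well.

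**Step 2: effect on 3-year OS (illustration).** Let u be the unoperated share of N = 50, and S_op and S_un the 3-year OS of operated and unoperated patients. All three are assumptions.

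- All enrolled: S_all = [(1 − u) × 50 × S_op + u × 50 × S_un] / 50
- Overstatement: S_op − S_all = u × (S_op − S_un)

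With S_op = 70% and S_un = 30%:

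- u = 10% (5 patients): (45 × 0.70 + 5 × 0.30)/50 = 33/50 = 66%; overstatement 4 points
- u = 20% (10 patients): (40 × 0.70 + 10 × 0.30)/50 = 31/50 = 62%; overstatement 8 points
- u = 30% (15 patients): (35 × 0.70 + 15 × 0.30)/50 = 29/50 = 58%; overstatement 12 points

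Other assumed pairs over the same range of u:

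- 70%/50%: 0.10 × 20 to 0.30 × 20 = 2 to 6 points
- 80%/20%: 0.10 × 60 to 0.30 × 60 = 6 to 18 points

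The sum uses one 3-year rate for operated patients whichever clock applies. Three years from enrolment end earlier than three years from surgery, so the operated patients' rate from enrolment would be the same or somewhat higher, and the true gap somewhat smaller.

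**Step 3: event-free survival (illustration).** Assume 60% of operated patients are event-free at 3 years and count failure to reach surgery as an event. Over all enrolled the rate is 0.90 × 60% = 54%, 0.80 × 60% = 48% or 0.70 × 60% = 42%. The distance from 60% is a difference between two endpoints and is not a bias in DFS.

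**The case against.** **Entry may come after response.** The risk-minimising text in 2.4.2 (assessment of risks and benefits) speaks of choosing good responders through the admission criteria. Inclusion criterion 3 in 6.1 refers to patients receiving preoperative therapy, the abstract goes from enrolment to work-up to surgery, and 9.3.1 counts adverse events only after surgery. If entry follows response, a surgical time origin is largely coherent. This stands as a conflict with 5.1 and 7.1.1, and it is why the enrolment point must be settled first.

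**The secondary objective ends with lobectomy.** Sections 1.1 and 4 describe patients who go on to that operation, so survival from surgery fits the objective as worded. This also stands: the endpoints cannot be said to miss the objective. What remains is that the protocol enrols a wider group and names an event-free survival rate without defining it.

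**Stronger readings that the text does not support.**

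- A reader might infer that every survival endpoint is dated from surgery. Only the two 3-year rates in 9.1 are; OS and DFS in months have no stated origin.
- A reader might infer that unoperated patients get no follow-up. Sections 8.1 and 8.3 promise it; the fault is a schedule that cannot be applied to them.
- A reader might infer that event-free survival is impossible to obtain. Patients are reassessed before surgery and withdrawal reasons are recorded, so it is undefined and not reliably obtainable.
- A reader might infer that DFS from surgery is wrong. In resected patients it is a legitimate measure.
- A reader might infer that nobody can reach the 3-year post-operative visit, because participation lasts 3 years. Nothing says that those years run from consent.

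**Conclusion.** The point holds where enrolment precedes chemoimmunotherapy, as 5.1 and 7.1.1 say. Enrolled patients who never reach surgery then have no time zero in the two defined 3-year rates and no workable visit schedule, and the abstract's event-free survival is left without a definition.

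The consequence is for OS. Applying 9.1 as written leaves these patients out, and the result flatters the strategy if they fare worse. The size cannot be taken from the protocol. It is 4-12 points under the 70%/30% assumption with 10-30% unoperated, and 2-18 points over the three pairs tried, before the small offset from the different clocks. If few patients miss surgery, or if those who do survive about as long, the effect is small.

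This should be fixed, but it does not threaten the main result: the R0 rate that 5.2 and 9.1 name as primary is unaffected. Section 10.2 places OS under the primary endpoints; that is a separate conflict, and it adds to the reasons for a clear OS origin.

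**What to change.** 1. State one enrolment point, and reconcile the selection of good responders in 2.4.2 with 5.1 and 7.1.1.
2. If enrolment precedes chemoimmunotherapy, define OS from enrolment in all enrolled patients. List event-free survival from the same date as a secondary endpoint in 5.2, 9.1 and 10.2, with progression precluding surgery, recurrence and death as events.
3. Keep DFS from surgery, labelled as a measure in resected patients.
4. For patients without surgery, date status contacts from enrolment, using the telephone and outpatient follow-up already in 8.3.
5. As a clarification of wording only, say whether the 3 years of participation run from consent or from surgery.

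The cost is protocol wording, a few extra status contacts for the patients not operated on, and survival figures that are likely to be slightly lower. The status contacts should be in place before patients reach the reassessment, since missed pre-surgical outcomes may be hard to recover.

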## 7.5 Commitment to research intervention

During the perioperative period, relevant complications and examination test results were recorded by the treating doctors and nursing staff, and after discharge, a specialized After discharge from the hospital, specialists will be assigned to conduct follow-up visits and record them in the case report form (CRF).

	screening period	Peri-operative period	Follow-up							
			3 months	6 months	9 months	1 year	1.5 years	2 years	2.5 years	3 years
Informed consent	×									
Base-line	×									
Inclusion/exclusion	×									
Test	Physical Examination	×	×							
	Complete Blood Count	×	×	×	×	×	×	×	×	×
	Blood Biochemical Analysis	×	×	×	×	×	×	×	×	×
	Tumor Bio-marker	×	×	×	×	×	×	×	×	×
	Chest CT	×	×	×	×	×	×	×	×	×
	PET-CT	×					×		×	
	Cephalic MR	×								

## 8. Discontinuation of the research intervention and discontinuation/withdrawal of research subjects

### 8.1 Discontinuation of the research intervention

The investigator should consider discontinuing the study intervention if the subject develops.

1) patients with serious unintended adverse reactions or complications that do not improve significantly after symptomatic treatment and cannot be continued. patients who are unable to continue the study intervention.

2) Patients who are unable to tolerate the study intervention for non-treatment related reasons.

3) Laboratory test values that, in the judgment of the investigator, are clinically significant. After discontinuation of the study intervention, patients may continue to complete other parts of the treatment regimen, including chemotherapy, radiotherapy, targeted therapy, immunotherapy, etc., and will be treated in accordance with the study protocol. therapy, targeted therapy, immunotherapy, etc., and will be scheduled for examination and follow-up according to the study protocol.

### 8.2 Suspension/withdrawal of research subjects

The researcher may discontinue or withdraw a research subject if the subject is.

1) pregnancy

- 2) apparent noncompliance with the study intervention.
- 3) if clinical side effects, abnormal laboratory tests, or other clinical conditions occur that make continued participation in the study is no longer in the best interest of the subject.
- 4) Disease progression such that discontinuation of the study intervention is warranted.
- 5) The subject meets the exclusion criteria (emerging or confirmed).
- 6) the subject is unable to receive the study intervention for a certain period of time.

The reason for discontinuation/withdrawal of the subject from the study should be documented on the case report form, and subjects who signed the informed consent, were randomized, but did not receive the study intervention will be replaced. Subjects who signed informed consent, were randomized, received the study intervention and were subsequently withdrawn will or will not be replaced.

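### Section 8.2 allows withdrawal and replacement on outcome-related grounds with no stated follow-up, so conversion failures can leave the R0 denominator and overall survival can be censored informatively

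*Protocol*

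**What the plan says.** Protocol section 8.1 deals with stopping the study intervention. Patients who stop may go on to other treatment and "will be scheduled for examination and follow-up according to the study protocol". Disease progression is not among the grounds listed there.

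Section 8.2 is a separate rule on taking a subject out of the study. It is permissive: "The researcher may discontinue or withdraw a research subject if the subject is" in one of six listed situations. Those that bear on outcome are:
- side effects, abnormal tests or other clinical conditions (ground 3);
- "Disease progression such that discontinuation of the study intervention is warranted" (ground 4);
- "the subject is unable to receive the study intervention for a certain period of time" (ground 6), with the period left undefined.

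The only record that 8.2 asks for is the reason: "The reason for discontinuation/withdrawal of the subject from the study should be documented on the case report form". It then turns to replacement. Subjects who gave consent, "were randomized, but did not receive the study intervention will be replaced". Those who "received the study intervention and were subsequently withdrawn will or will not be replaced", which leaves the matter open.

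Section 8.3 plans 3 years of telephone and outpatient follow-up and does not mention withdrawn subjects. Section 9.1 defines the primary endpoint as the proportion of patients whose tumor is completely removed by lobectomy, with no further statement of the denominator. Its survival endpoints run from surgery, for example "3-year overall survival rate: defined as the proportion of patients who are still alive 3 years after surgery".

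**The concern.** The strategy under test is chemoimmunotherapy followed by lobectomy in patients who would otherwise need pneumonectomy. A patient who progresses, suffers toxicity or becomes inoperable before surgery is a result of that strategy, and an unfavourable one. Section 8.2 treats these same events as reasons to leave the study. For patients who never receive the intervention, it also puts someone else in their place.

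Two results are exposed. The first is the primary endpoint: the R0-by-lobectomy rate can end up describing patients who got as far as the operation instead of those who entered the trial, and so make conversion look more feasible than it is. The second is overall survival: if 8.2 is used after surgery, a patient withdrawn at progression is censored just as the risk of death rises, and Kaplan-Meier assumes that censoring is unrelated to that risk.

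The study is open-label and single-arm at four centers (section 5.1). Sites may use the option differently, and no comparator would reveal it. An analysis plan cannot recover vital status that was never collected.

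**Working it through.** There is no figure of the plan's own to reproduce. Section 5.3 sets 50 patients without a calculation, and the protocol gives no expected R0 rate, event rate or dropout rate. The check therefore follows the text through each endpoint and illustrates size under stated assumptions.

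**Step 1. Which patients 8.2 reaches.** Section 8.1 describes chemotherapy, radiotherapy, targeted therapy and immunotherapy as other parts of the treatment regimen, which points to surgery as the intervention. On that reading, grounds 4 and 6 act mainly before surgery, and a patient who is never operated on falls under the replacement rule. Section 7.1.1, however, describes adjuvant treatment under the intervention heading. On that reading, ground 4 can also act after surgery.

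**Step 2. R0 by lobectomy (before surgery).** Let x be the successes among 50 analysed patients and w the number withdrawn and replaced, none of whom had an R0 lobectomy. The reported rate is x/50. The rate over everyone enrolled is x/(50 + w). The values of x and w are assumptions.

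| x | w | x/50 | x/(50 + w) | Difference (points) |
|---|---|---|---|---|
| 40 | 3 | 80.0% | 40/53 = 75.5% | 4.5 |
| 40 | 5 | 80.0% | 40/55 = 72.7% | 7.3 |
| 40 | 10 | 80.0% | 40/60 = 66.7% | 13.3 |
| 30 | 3 | 60.0% | 30/53 = 56.6% | 3.4 |
| 30 | 5 | 60.0% | 30/55 = 54.5% | 5.5 |
| 30 | 10 | 60.0% | 30/60 = 50.0% | 10.0 |

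The exact 95% interval for 40/50 is 66.3% to 90.0%; for 40/60 it is 53.3% to 78.3%. If withdrawn patients are dropped without being replaced, the direction is the same: 30/50 = 60.0% becomes 30/45 = 66.7% when 5 are left out.

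**Step 3. Overall survival (only if 8.2 is used after surgery).** Assumptions, none from the protocol:
- exponential times;
- progression by 36 months 40% (range 30 to 50%);
- median survival after progression 18 months (range 12 to 24);
- death without progression 10% by 36 months.

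With progression hazard λ, hazard of death without progression d and hazard of death after progression μ, true survival at 36 months is

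S = e^(−36(λ+d)) + λ[e^(−36(λ+d)) − e^(−36μ)]/(μ − λ − d).

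Central case: λ = −ln(0.6)/36 = 0.01419, d = −ln(0.9)/36 = 0.00293, μ = ln(2)/18 = 0.03851. Then S = 0.540 + 0.01419 × (0.540 − 0.250)/0.02139 = 0.540 + 0.192 = 0.732.

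Kaplan-Meier estimates were simulated with 1,000,000 patients per scenario and a share of progressors censored at progression:

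| Share of progressors withdrawn | Estimated 3-year OS, central case | Upward bias, central case (points) | Upward bias, whole range (points) |
|---|---|---|---|
| None | 73% | 0 | 0 |
| Half | 80% | 7 | 4 to 11 |
| All | 90% | 17 | 10 to 27 |

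The last row is a limit. The 90% only returns the assumed 10% death without progression.

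**Step 4. Disease-free survival.** Section 9.1 makes recurrence or metastasis the event. Withdrawal at a recorded recurrence comes after that event has been counted, so DFS does not rise. DFS is exposed only when a patient is withdrawn on another ground, such as non-compliance or side effects, before recurring.

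**Step 5. Patients lost before surgery.** OS and DFS run from surgery, so these patients never enter those curves. For them the effect is on the R0 rate alone.

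**The case against.** The strongest case against has four parts.

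- **Withdrawal is optional, and no sentence says that withdrawn subjects leave follow-up.** This stands. A reader might infer that 8.2 certainly removes progressing patients and biases the results. The text does not go that far: 8.1 keeps follow-up after the intervention stops, ground 4 is itself worded as such a stop, and 8.3 promises 3 years without exception. What remains is two unreconciled sections, of which only one keeps patients in follow-up.
- **Ground 4 fits the period before surgery best.** This largely stands and limits the survival argument. Once the operation is done there may be little intervention left to discontinue, unless adjuvant care counts. The OS bias is therefore conditional.
- **DFS.** A reader might infer that withdrawal for progression inflates DFS as well. The documents do not support this, because a recorded recurrence is already the event.
- **Analysis populations belong in an analysis plan, and this is a 50-patient study without a hypothesis-based sample size.** This stands only in part. How a withdrawn patient is analysed could be set elsewhere. Who is replaced, and whose vital status is collected, are rules of conduct that the protocol itself sets.

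**Conclusion.** The point holds as a risk of upward bias arising from the wording of 8.2. The firmer part concerns the primary endpoint: followed as written, 8.2 allows patients who fail before surgery to be replaced, and section 9.1 does not put them back in the denominator. With 3 to 10 such patients and an apparent R0 rate of 60% or 80%, the overstatement is about 3 to 13 points. These counts are assumed.

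The weaker part concerns overall survival. It requires 8.2 to be applied after surgery and follow-up to stop there. The range of 4 to 11 points at 3 years rests wholly on assumed event rates and on half of progressors being withdrawn. The larger figures need every progressor to be withdrawn under an optional rule and should not be read as expected. No upward bias in DFS follows from withdrawal at recurrence.

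**What to change.** - Reconcile 8.1 and 8.2 so that stopping the study intervention does not by itself end data collection. Which clinical grounds justify stopping is for the investigators to settle.
- State that recurrence and vital status are collected to 3 years for every subject unless the subject withdraws consent.
- Define the R0-by-lobectomy denominator as all enrolled patients, and count any patient without an R0 lobectomy as a failure, whatever the reason.
- Delete or settle the replacement sentences. The reference to randomization does not fit a single-arm trial, and the alternative left open for subjects withdrawn after the intervention needs a decision. If replacement is kept, say that replaced patients remain in the primary analysis.

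The cost is a wording amendment and a few more follow-up contacts, since the telephone and outpatient follow-up in 8.3 already exists. The R0 and overall survival figures may come out somewhat less favourable.
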